#### 9.1.2.10 QUALITY OF LIFE (QOL)

Generic and disease-specific measures will be used to assess quality of life.

##### **Generic Measures**

Version 2 of the SF-36® Health Survey, standard (4-week) recall form.

This widely used, generic instrument derives eight scales (physical functioning, role-physical, bodily pain, general health, vitality, social functioning, role-emotional, mental health) and two summary components (physical and mental). Changes to version 2 in relation to version 1 include simplified wording, simplified layout, and changes to the number of response options to selected items. Additionally, current normative data for version 2 are based on more recent, 1998 general US population data and norm-based scoring has been developed for the eight individual scales in addition to the summary components (for which it was available in version 1). The current manual contains US population norms by gender and age group within gender. The publisher states that the next printing, which is scheduled for the fall of 2005, will contain disease-specific norms including diabetes and kidney disease. If the 36-item version of the instrument were felt to be too lengthy, version 2 of the SF-12 (standard recall form) would be an option. This shorter version would derive eight scales and two summary components and would be also be normed to the 1998 data (general population and disease-specific groups).

### EQ-5D (EuroQoL)

This instrument is a utility measure that generates a descriptive profile and single index value for health status. The descriptive portion addresses five health dimensions (mobility, self care, usual activities, pain/discomfort, and anxiety/depression) with respondents indicating one of three possible responses for each dimension. Summary data can be reported as the proportion of respondents with problems in each dimension. Additionally, the multidimensional “health state” can be converted to a single weighted health status index that reflects the valuation of various possible health states from general population samples, including one that has been developed in a nationally representative US sample. The second portion of the EQ-5D is a (0-100) visual analogue scale that is used to report overall health status. Advantages of this instrument include its brevity and particular application in cost-effectiveness research. The EQ-5D is a public domain instrument. Projects may be registered and instruments obtained through the EQ-5D website, [www.euroqol.org](http://www.euroqol.org).

### Disease-targeted Measures

#### Diabetes Distress Scale

The Diabetes Distress Scale (DDS) represents the latest iteration of the Problem Areas in Diabetes (PAID) scale. This is a 17-item self-administered questionnaire culled from a longer battery of 28-items. Psychometric properties for the DDS were recently published in *Diabetes Care* (March 2005). The DDS measures four diabetes-related distress domains: emotional-burden (EB), physician-related interpersonal distress (PD), regimen-related distress (RD), and diabetes-related interpersonal distress (ID). Internal consistency as measured by Cronbach’s coefficient alpha ranged between 0.88 and 0.93 for the multi-item scales. The developers tested for and demonstrated construct validity using exploratory factor analysis.

#### Hypoglycemic Fear Survey

The Hypoglycemic Fear Survey (HFS) is a 23-item self-administered survey for measuring the fear experienced with respect to hypoglycemia. The HFS measures hypoglycemia avoidance behavior and worry about hypoglycemia. Different versions of the instrument can be found in the literature, varying in length from 15 to 33 items. We have used the 33-item recommended by [name]. Coefficient alpha for the behavioral and the worry scales were found to exceed 0.90.

## 9.2 Immunologic Testing

Although insulin independence can be achieved via transplantation of an adequate number of viable, functional islets, a gradual reduction in the percent insulin independent patients occurs over time, with approximately 25% of patients still insulin free at 4 years post-transplant. Immune mediated islet destruction in the form of allo-rejection and/or recurrent autoimmunity, as well as attrition of a marginal islet mass due to exhaustion and/or toxicity of immunosuppressive agents, have all been postulated to play a role in islet loss. In order to begin to dissect the role of immune mediated reactions in allograft loss, tests will be done to determine if sensitization to donor allo- or islet autoantigens has occurred. In addition,

maintenance of protective immunity in the setting of immunosuppression will be addressed, as will the role of innate immune reactions in the early post-transplant period.

While methods for determination of allo- and autoantibody have been extensively studied and are fairly well-established, reliable, reproducible and validated methods for assessment of T cell immunoreactivity to allo and/or autoantigens do not exist. For the most part, these techniques are time-consuming, technically demanding and require large blood volumes and significant staff time for set up and analysis of the resultant data. Several methods are undergoing testing in multiple T1D consortia (e.g., ELISPOT, tetramer staining, T cell proliferation assays) to determine which tests provide the most reliable data with regards to distinguishing between patients with T1D vs. normal controls (for autoantigen) and to improve techniques for assessing recipient anti-donor reactivity.

### **9.2.1 Immune Assays**

#### **9.2.1.1 HLA TYPING OF DONORS AND RECIPIENTS, CROSSMATCHING**

HLA typing of donors and recipients, as well as crossmatching, will be done at individual centers. A negative crossmatch is required in order for transplantation to occur.

#### **9.2.1.2 ALLOANTIBODY**

Development of alloantibody is generally associated with longer term graft loss. Development of alloantibody specific for 1 or 2 HLA antigens can now be defined using assays that incorporate HLA specific monoclonal antibodies. [name] at Penn will provide core lab service for alloantibody assessments.

#### **9.2.1.3 AUTOANTIBODY**

The role of autoantibody in graft loss remains unclear. [name]'s lab in Denver will provide core lab service for autoantibody assessments.

#### **9.2.1.4 ARCHIVED SAMPLES**

In order to ensure that we will ultimately gain as much information as possible from these trials, and due to the ongoing development of assays such as T cell assays, serum and plasma will be archived for future analyses. Details for subjects regarding the archiving of samples and use for future assays are contained in the study's informed consent form. Subjects will have the option of whether or not they want to have samples archived and will indicate their choice on the informed consent form. A subject's choice regarding archiving samples will not affect his/her participation in the study.

Serum: Blood will be collected to obtain serum and archived in the NIDDK repository.

Plasma: Blood will be collected, processed and archived in the NIDDK repository.

#### 9.2.1.5 IMMUNOGENICITY DETERMINATION

Anti-belatacept antibody and immunogenicity testing will be performed during the study. Immunogenicity samples should also be taken 4 and 8-weeks post last dose for subjects discontinued from belatacept. Samples must be taken prior to beginning the infusion of belatacept.

## **10. STATISTICAL CONSIDERATIONS AND ANALYTICAL PLAN**

### **10.1 Analysis Samples**

The details of the analyses will be provided in the statistical analysis plan (SAP). All primary and secondary analyses will be done using the intention to treat principal. Every subject who receives belatacept or islets will be accounted for in the analysis.

### **10.2 Study Endpoint Assessment**

#### **10.2.1 Primary Endpoint**

The primary objective of the analysis is to estimate the rate of insulin independence at 75 days after the first islet transplant. The primary endpoint is insulin independence (yes/no) at day 75 after islet transplant as defined in section 4.1.1. The primary analysis will compute an exact binomial estimate and a 95% confidence interval for the true rate. If the results of this trial show at least 10% insulin independence in the context of evaluation all of the secondary endpoints, the investigators will consider this grounds for further investigation.

The primary analysis will consist of the intent-to-treat population. An exception will be if a death occurs or if the subject withdraws consent to be followed, in these cases the endpoint will be classified as failure to achieve insulin independence. Should the endpoint not be evaluated for a particular individual for other reasons, a failure will be imputed unless an evaluation is done at a time longer than 75 days after transplant and before an additional islet transplant, in which case that later value will be imputed. All imputations will be reported with the primary analysis.

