## Study Definitions

Full Graft Function	Islet transplant recipients will be considered to have full islet graft function if they are insulin independent.
Graft Failure	Islet allograft failure will be defined as absence of insulin production by transplanted islets, as evidenced by c-peptide < 0.3 ng/mL. This will be determined by (1) c-peptide < 0.3 ng/mL on random testing, followed by (2) c-peptide < 0.3 ng/mL at baseline, and at 60 and 90 minutes after MMTT. C-peptide levels obtained in the course of the MMTT will be run at the core lab in Seattle, WA; allow 72 hours for results. Participants with graft failure do not need to complete the day 75 metabolic assessments.
Insulin Independent	
Subjects will be considered insulin independent if they are able to titrate off insulin therapy for at least 1 week and all of the following criteria are met:
 

• One HbA1c level, one fasting serum glucose level, and a Mixed Meal Tolerance Test are documented within the visit window (e.g. 70-80 days at Day 75) and 7 consecutive days of blood sugar and insulin readings are documented within +/- 7 days of the visit window (e.g. 63 - 87 days at Day 75);

• HbA1c < 7.0% or ≥ 2.5% decrease from baseline;

• Fasting capillary glucose level should not exceed 140 mg/dL (7.8 mmol/L) more than three times in 7 consecutive days (fasting is defined as 1st blood sugar reading of the day not noted as post-prandial or bedtime);

• Post-prandial serum glucose ≤ 180 mg/dL (10.0 mmol/L) at 90 minutes during the MMTT;

• Fasting serum glucose level ≤ 126 mg/dL (7.0 mmol/L); if the fasting serum glucose level is > 126 mg/dL (7.0 mmol/L), it must be confirmed in an additional one out of two measurements;

• At least one MMTT fasting or stimulated c-peptide ≥ 0.5 ng/mL.

Insulin Dependent	Islet transplant recipients who do not meet the criteria for insulin independence will be considered insulin dependent.
Intensive Diabetes Management	Self monitoring of glucose values no less than a mean of three times each day averaged over each week and by the administration of three or more insulin injections each day or insulin pump therapy.
Partial Graft Function	Islet transplant recipients who do not meet criteria for insulin independence, but have either a basal or stimulated c-peptide level ≥ 0.3 ng/mL (0.1 nmol/L).

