## 4.1 Study Endpoints

### 4.1.1 Primary Endpoint

The primary endpoint for this study is the proportion of **insulin-independent** subjects at day 75 ( $\pm 5$  days) following the first islet transplant.

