### 7.6.1 Second Islet Transplant

Islet transplant recipients with partial islet graft function (see Study Definitions) will be considered for a second islet transplant in the interim between 85 days and 8 months post-initial infusion. Islet transplant recipients with **graft failure** will be considered for a second islet transplant before 85 days post-initial infusion. In addition to meeting the criteria outlined below, approval from the Steering Committee must be obtained in advance. Please refer to the MOP for details on this process, which includes review of the potency testing from the first transplant product and post-transplant clinical data.

In order to be eligible for a **second islet transplant**, the following requirements must be met:

1. Subject received  $\geq 5,000$  IE/kg with the first transplant, but failed to achieve or maintain insulin independence.
2. Subject has been compliant with study monitoring and prescribed immunosuppressive therapy.
3. Subject has no unresolved SAEs.
4. No evidence of progressive renal dysfunction, with blood creatinine rising above 2.0 mg/dL (177  $\mu$ mol/L).
5. No evidence of hypersensitization, allergic responses, or other potentially serious drug reactions to medications required by the protocol.
6. PRA  $\leq 50\%$  by flow cytometry (assessment performed locally) and the alloantibody specificity not cross-reactive with antigen(s) present in the subsequent islet preparation in order to avoid unacceptable antigen(s).
7. Absence of any medical condition that, in the opinion of the investigator, will interfere with a safe and successful second islet transplant.

If graft failure occurs after the second islet transplant, these recipients will be considered **treatment failures** with no islet graft function, and immunosuppression will be withdrawn.

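### A missing Day 75 primary result may be replaced by an evaluation from any later day before a further transplant, with no latest day and no rule for choosing among several

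*Protocol*

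**What the plan says.** Section 4.1.1 measures a proportion at a fixed time ("The primary endpoint for this study is the proportion of"): those who are insulin independent at Day 75 ± 5 after the first transplant. Section 10.4 repeats that the aim is to estimate the rate at 75 days, in 10 subjects.

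The Study Definitions set the timing of the components. HbA1c, fasting serum glucose and the MMTT must fall inside the visit window (Days 70 to 80), while "7 consecutive days of blood sugar and insulin readings are documented within +/- 7 days of the visit window", that is, Days 63 to 87.

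Section 10.2.1 handles missing results in two steps:

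- Death and withdrawal of consent: "if a death occurs or if the subject withdraws consent to be followed, in these cases the endpoint will be classified as failure".
- Any other reason: the subject is scored as not insulin independent, "unless an evaluation is done at a time longer than 75 days after transplant and before an additional islet transplant". Where such an evaluation exists, its result, whether success or failure, becomes the Day 75 result.

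It adds: "All imputations will be reported with the primary analysis". The same section says that at least 10% insulin independence, read together with the secondary endpoints, would be grounds for further investigation.

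**The concern.** The substitution has a start (after Day 75) and one end (a further transplant), but no latest day. For a subject who is never retransplanted, only the end of follow-up closes it, and section 7.5 sets follow-up at 24 months after the final transplant. If several later evaluations exist, the rule does not say whether the first, the last or the most favourable one counts.

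Missing Day 75 results are plausible. Three laboratory assessments must fall within 11 days, and section 9.1.2.5 reschedules the MMTT when the capillary glucose is below 70 or above 180 mg/dL. That cause of delay may itself be related to graft function.

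At stake is what the primary estimate means. Insulin independence changes over time. A status found at Day 196 or Day 365 is a different quantity from status at Day 75, and in a trial of 10 subjects one such value is visible in the headline rate.

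**Working it through.** **1. The plan's own intervals.** Table 5 in section 10.4 gives exact 95% limits for x of 10. The Clopper-Pearson formula reproduces all 11 rows to the precision printed. For the two rows used here:

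- 0/10: upper limit = 1 − 0.025^(1/10) = 0.3085.
- 1/10: lower limit = 1 − 0.975^(1/10) = 0.0025; upper limit 0.445 (beta quantile).

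**2. How late a scheduled substitute would be.** In Appendix 1, HbA1c, MMTT and the blood sugar record appear together after transplant at Days 75, 196, 280 and 365. The last three visits have windows of ± 5 days.

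| Visit | Nominal delay after Day 75 | Earliest in window |
|---|---|---|
| Day 196 | 196 − 75 = 121 | 191 − 75 = 116 |
| Day 280 | 280 − 75 = 205 | 275 − 75 = 200 |
| Day 365 | 365 − 75 = 290 | 360 − 75 = 285 |

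These are scheduled delays. The rule asks only for an evaluation, so a Day 75 visit held a few days late would also qualify.

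**3. Effect compared with missing = failure.** A late success adds 1/10 = 0.10 to the rate; a late failure adds 0. The rate rises or stays the same.

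| Observed successes | Late successes | Rate (95% CI) |
|---|---|---|
| 0 | 0 | 0.0 (0 to 0.3085) |
| 0 | 1 | 0.1 (0.0025 to 0.445) |
| 3 | 0 | 0.3 (0.0667 to 0.6525) |
| 3 | 1 | 0.4 (0.1216 to 0.7376) |
| 5 | 0 | 0.5 (0.1871 to 0.8129) |
| 5 | 1 | 0.6 (0.2624 to 0.8784) |

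**4. Effect compared with true Day 75 status.** Let p be the probability of independence at Day 75, a the probability of being independent later given independence at Day 75, and b the probability of being independent later given dependence at Day 75. A substituted value is a success with probability q = p·a + (1 − p)·b. With m of 10 subjects substituted, the expected bias is (m/10)·(q − p). The protocol gives none of p, a, b or m, so these are assumptions. With m = 2 and p = 0.5:

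- a = 1.0, b = 0.2: q = 0.60, bias = 0.2 × 0.10 = +0.02.
- a = 0.8, b = 0.2: q = 0.50, bias = 0.
- a = 0.6, b = 0: q = 0.30, bias = 0.2 × (−0.20) = −0.04.

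For a pessimistic value of a, section 1.4.1.1 reports independence at one centre falling from 72% at one year to 28% by three years, and 28/72 = 0.39. That is an illustration over a longer interval, not an estimate for this trial. Over p = 0.3 to 0.7, a = 0.39 to 1.0 and b = 0 to 0.2, the bias runs from −0.086 to +0.028.

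**The case against.** **Safeguards.** Death and withdrawal of consent are failures. Appendix 1 uses results from the time of graft failure for the Day 75 calculation. All imputations are reported, so with 10 subjects a reader can undo each one. The 10% level is a soft pilot signal read with the secondary endpoints, and no hypothesis is tested. All of this stands and limits the harm, but disclosure still leaves the substituted value in the headline estimate.

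**The SAP.** Section 10.1 leaves analysis details to the SAP, which is not shown and may set a limit. But section 10.2.1 does not defer this rule; it states it, open-ended.

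**Stronger readings that the documents do not support:**

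- *A reader might infer that the rule can only inflate the rate.* That holds only against missing = failure. A subject who was independent but unevaluated at Day 75, and has lost independence by Day 196, is scored a failure and lowers the rate.
- *A reader might infer selection by retransplantation*, because partial-function recipients "will be considered for a second islet transplant in the interim between 85 days and 8 months post-initial infusion". But an unevaluated subject who is retransplanted with no prior late evaluation stays in the denominator as a failure.
- *A reader might infer that sites could delay the assessment of a subject still tapering insulin.* Nothing documents this. Under the Study Definitions such a subject fails the requirement of at least a week off insulin, and can arguably be classed as dependent from the insulin record alone. Section 7.6.1 also makes compliance with monitoring a condition of a second transplant.
- *A reader might take 121 days as the minimum delay.* The visit window shortens it to 116, and an unscheduled or slightly late assessment could come sooner still.

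**Conclusion.** The point holds as a defect in how the rule is fixed. Section 10.2.1 allows a status from months later to be entered as the Day 75 result, without a latest day and without a choice among later values. The primary estimate can then mix two quantities.

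Each substitution moves the rate by up to 10 percentage points. One late success turns 0/10 into 1/10 and reaches the 10% level, though that level alone decides nothing. Relative to missing = failure, the effect is upward or nil. Relative to true Day 75 status, the sign is unknown, and the range in the working rests on assumed values of p, a, b and m. The protocol states no missing-data rate, so the expected number of substitutions cannot be given.

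**What to change.** In section 10.2.1, and correspondingly in the SAP:

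- State a latest acceptable day close to the window. Day 87 is workable: it is the outer limit already used for the 7-day glucose and insulin record (80 + 7) and the end of the Day 84 ± 3 visit window in Appendix 1 (84 + 3). It is not an existing limit for HbA1c, fasting glucose or the MMTT, which the definition holds to Days 70 to 80, so it should be adopted explicitly as the cut-off for substitution.
- Use the first complete evaluation after the window, up to that day and before any further transplant. Otherwise impute failure.
- Show results that use later values only as a sensitivity analysis.

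The cost is a short text change and one extra table, with no new visits. The downside is that a few late assessments will count as failures, so the reported rate may be slightly less favourable.

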#### **10.2.2 Secondary Endpoints**

Secondary endpoints are defined in section 4.1.2. There are a very large number of secondary endpoints so there will be no adjustment for multiplicity. We will not impute values for secondary endpoints but will conduct a sensitivity analysis to determine the potential magnitude of the contributions of the missing values. Details of the sensitivity analysis will be included in the SAP.

Analysis of secondary endpoints will use methods similar to those defined for the primary outcome. When the endpoint is a proportion such as patients achieving insulin independence at one year after completing their first islet transplant then the observed rate will be used as the point estimate and an exact 95% binomial confidence interval will be reported. Continuous variables will be treated in a similar fashion. If the necessary normality assumption is valid then the sample mean will be used as the point estimate and the usual 95% normal confidence intervals will be computed. Where the normality assumptions are not valid and an appropriate transform will achieve normality then the inverse of the mean of the transformed data will be used as the point estimate and the inverse of the endpoints for a standard 95% confidence interval for the transformed mean will be reported for the confidence interval. If no valid

transformation can be found then we will use the bootstrap method to construct a point estimate and a 95% confidence interval.

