#### 5.7.2 Premature Discontinuation of Study Treatment (Transition to “Off-Protocol” Treatment)

Study treatment may be prematurely discontinued for any subject for any of the following reasons:

1. The subject is unwilling or unable to comply with the protocol.
2. The investigator believes that the study treatment is no longer in the best interest of the subject.
3. Graft Failure (see Study Definitions).
4. Any clinical AE, laboratory abnormality, or intercurrent illness which, in the opinion of the investigator, indicates that continued treatment with study therapy is not in the best interest of the subject. The agent(s) to which the event is attributed will be discontinued.
5. The subject becomes pregnant
6. Missing 2 consecutive belatacept infusions
7. The development of belatacept is terminated by the manufacturer (BMS)
8. The subject is imprisoned or compulsorily detained for the treatment of either a psychiatric or physical illness (e.g., infectious disease).

Subjects who prematurely discontinue study treatment will remain in the study until normal termination, for the purpose of monitoring safety and efficacy parameters and will enter the reduced follow-up scheduled outlined in Appendix 5. Data from these subjects will be used in the intent-to-treat analysis. These subjects are permitted to simultaneously enroll in a CIT or site-specific graft failure follow-up protocol, if available.

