### **7.5 Follow-up Visits**

Subject will undergo a 24-month follow-up period following their final islet transplant. Please refer to the Schedule of Events (Appendices 1, 2, 3, and 4), for the clinical time points of specific follow-up study procedures.

All subjects will follow the Year One Schedule of Events (Appendix 1) in its entirety. Subjects who receive a subsequent islet transplant will continue onto Appendix 2, Continuation of Appendix 1 Schedule of Events (Subjects with Subsequent CIT Transplants) until they reach their one year visit after the final islet transplant. In addition to following Appendix 2, all

subjects who receive a subsequent transplant should complete the assessments listed on the Subsequent Transplant Schedule of Events (Appendix 3), which provides immediate post-transplant and endpoint day assessments. After the one year post-final transplant visit, subjects will move to Appendix 4, Schedule of Events for 1-Year Additional Follow-up.

Subjects are ineligible for subsequent islet transplantation in the CIT04 protocol as of 8 months following their initial transplant (between visits 16 and 17). After visit 21 (365 days following transplant) has been completed, study subjects may obtain a subsequent islet transplant outside of CIT04. Subjects will be followed for adverse events only until until 24 months after their final CIT islet transplant.

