## 10.4 Sample Size and Power Calculations

The purpose of this pilot study is to estimate the true rate of insulin independence at 75 days. The selected sample size is 10 subjects. The point estimate of the true insulin independence rate will be the proportion of the 10 patients that achieve insulin independence. The precision of the estimate depends on the observed number of subjects achieving insulin independence. The following table displays the confidence intervals that would be computed for each possible outcome. If 5 of the 10 subjects achieve insulin independence then the estimated rate will be 50% and a 95% confidence interval will be 0.1871 to 0.8129. That is, we are 95% confident that the true rate is at least 18.71% and no more than 81.29%. The confidence interval rules out any rate less than 18.71% or greater than 81.29%. If 3 patients (30%) achieve insulin independence, then the confidence interval will rule out any rate less than 6.67% or greater than 65.25%.

*Table 5: Confidence Intervals for each possible outcomes*

Number of Subjects insulin Independent at 75 Days	Estimated Rate	Exact 95% Confidence Interval	
		Lower Bound	Upper Bound
0	0	0	0.3085
1	0.1	0.0025	0.445
2	0.2	0.0252	0.5561
3	0.3	0.0667	0.6525
4	0.4	0.1216	0.7376
5	0.5	0.1871	0.8129
6	0.6	0.2624	0.8784
7	0.7	0.3475	0.9333
8	0.8	0.4439	0.9748
9	0.9	0.555	0.9975
10	1	0.6915	1

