### *Appendix 5: Reduced Follow-up Schedule of Events*

Subjects withdrawn from study therapy should be followed according to the reduced follow-up schedule provided below. All reduced follow-up assessments should be scheduled relative to the day on which the study treatment is discontinued. The last follow-up visit will vary depending on when the subject discontinues study therapy and should be done at 1 year post the subject's **last** transplant.

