#### **REDUCED FOLLOW-UP SCHEDULE**

Complete the following assessments at the intervals (+/- 7 days) indicated below relative to the day the subject discontinued study treatment. Continue conducting these assessments at the defined intervals until the subject reaches two years post **last** transplant.

- Assess SAEs and hypoglycemic events: q1 month. If subject does not come to the study site for the visit, attempt to obtain information via a phone contact.
- Alloantibody (central lab): q 1 month for the first 3 months and q 3 months thereafter.
- Immunogenicity Samples: for subjects who discontinue belatacept, collect samples at 4 weeks and 8 weeks post last dose

Complete the following assessments at 1 and 2 years (+/- 14 days) post **initial** transplant:

- Assess SAEs and hypoglycemic events
- Alloantibody (central lab)
- HbA1c (central lab)
- 90 minute c-peptide post MMTT (central lab)
- Serum creatinine (central lab)
- QOL questionnaire (via mail or in-person)

Complete the following assessments at 1 and 2 years (+/- 7 days) post **last** transplant:

- Assess SAEs and hypoglycemic events
- QOL questionnaire (via mail or in-person)

*Appendix 6: Study Contacts*

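### Secondary responder rates have a no-imputation rule and no failure rule, so subjects without a value probably leave the denominator; for re-transplanted subjects off treatment the HbA1c schedules also conflict

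*Protocol*

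**What the plan says.** Section 4.1.2 names two secondary responder endpoints: the proportion with HbA1c below 7.0% and no severe hypoglycemic event from Day 28 to Day 365, counted after the first transplant (the key secondary endpoint) and after the final transplant. Section 4.1.2.1 adds a favorable-outcome rate per islet-preparing center, using the same two components.

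For missing data, section 10.2.2 says "We will not impute values for secondary endpoints" and promises a sensitivity analysis, to be detailed in the SAP. For proportions, "the observed rate will be used as the point estimate and an exact 95% binomial confidence interval will be reported". Section 10.2.1 treats the primary endpoint differently. Death and consent withdrawal are failures, and any other missing result is a failure unless a later evaluation exists before a further transplant. Section 10.1 applies intention to treat to all primary and secondary analyses and says every subject given belatacept or islets will be accounted for.

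Subjects who stop study treatment move to the reduced schedule in Appendix 5, and under section 5.7.2 "Data from these subjects will be used in the intent-to-treat analysis". Section 7.6.1 sends one such group there: "If graft failure occurs after the second islet transplant, these recipients will be considered" treatment failures, with immunosuppression withdrawn. Appendix 5 takes central HbA1c at 1 and 2 years after the initial transplant. Its separate list for the last transplant, opening "Complete the following assessments at 1 and 2 years (+/- 7 days) post", holds only SAEs, hypoglycemic events and the quality-of-life questionnaire.

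**The concern.** For a yes/no endpoint, no imputation combined with the observed rate most naturally means that a subject with no value is in neither the numerator nor the denominator. The subjects most likely to lack a value have died, withdrawn or stopped treatment, and they are mostly not successes. The responder rate would then describe the subjects who could still be measured, not all those treated, which does not fit section 10.1.

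This matters beyond description. Section 10.2.1 makes the judgment on further investigation depend on at least 10% insulin independence read in the context of all secondary endpoints, and these two responder rates head that list. In a trial this small, each subject dropped moves the estimate visibly.

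**Working it through.** **1. The plan's own interval.** "The selected sample size is 10 subjects" (section 10.4). Table 5 uses the exact binomial interval: lower limit = Beta quantile (0.025; x, n − x + 1), upper limit = Beta quantile (0.975; x + 1, n − x). With n = 10 this reproduces all 11 rows to four decimals; for example, 5/10 gives 0.1871 to 0.8129.

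**2. Effect of the denominator.** Let r be the number of responders and m the number of failures with no value. Counted as failures, the rate is r/10. Dropped, it is r/(10 − m). The documents give no value for m, so the range 0 to 4 is an assumption, as are the values of r.

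| m | r = 5 | Exact 95% CI | r = 3 |
|---|---|---|---|
| 0 | 5/10 = 50.0% | 18.7 to 81.3% | 3/10 = 30.0% |
| 1 | 5/9 = 55.6% | 21.2 to 86.3% | 3/9 = 33.3% |
| 2 | 5/8 = 62.5% | 24.5 to 91.5% | 3/8 = 37.5% |
| 3 | 5/7 = 71.4% | 29.0 to 96.3% | 3/7 = 42.9% |
| 4 | 5/6 = 83.3% | 35.9 to 99.6% | 3/6 = 50.0% |

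For r = 5, each further dropped failure adds about 6 to 12 points.

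**3. Can the Appendix 5 HbA1c serve the final-transplant endpoint?** I read that endpoint's HbA1c as the Day 365 value and use the ±14-day window of section 4.1.2.1. Let t be the day of the last transplant, counted from the first.
- HbA1c needed: days 351 + t to 379 + t.
- HbA1c scheduled in Appendix 5: 365 ± 14 = days 351 to 379, and 730 ± 14 = days 716 to 744.
- Overlap with the earlier window requires 351 + t ≤ 379, so t ≤ 28.
- Overlap with the later window requires 379 + t ≥ 716, so t ≥ 337. Sections 7.6.1 and 7.6.2 close re-transplantation at 8 months, about day 243.

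A second transplant for partial function falls between day 85 and about day 243. One year later is day 365 + 85 = 450 to day 365 + 243 = 608, clear of both windows. Only a re-transplant within 28 days of the first would be covered.

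**4. The competing schedule.** Section 7.5 tells all subjects with a subsequent transplant to complete Appendix 3, which lists central HbA1c at Day 365 ± 14 after the most recent infusion. The Appendix 3 footnote that stops collection after graft failure is attached to fasting glucose and c-peptide, FSIGT, MMTT, CGMS and the blood sugar record, not to HbA1c. So two instructions apply to the same subject: section 5.7.2 with Appendix 5 (no HbA1c then) and section 7.5 with Appendix 3 (HbA1c then).

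**5. End of reduced follow-up.** The opening paragraph of Appendix 5 has the last visit vary "depending on when the subject discontinues study therapy and should be done at 1 year post" the last transplant. The next paragraph continues assessments until two years after it.

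**The case against.** The strongest reply is that no sentence excludes anyone. Section 10.1 promises intention to treat, section 10.2.2 describes methods similar to those for the primary outcome, and the sensitivity analysis is left to a SAP that is not at hand. This has weight: the smaller denominator is inferred, and the SAP may state a rule. But the similarity in 10.2.2 is spelled out as point estimate and interval, whereas the missing-data sentence is specific and departs from the primary rule. As it stands, the protocol does not say how a subject with no value is counted in these rates.

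Several stronger readings are tempting, and the documents do not support them.
- A reader might infer that the schedule removes treatment failures from both endpoints. It does not. Appendix 5 takes HbA1c one year after the initial transplant, so the first-transplant endpoint is untouched by the gap, and for a single-transplant subject initial and last are the same.
- A reader might infer that the HbA1c is simply omitted for the rest. Appendix 3 requires it, so this is a conflict between schedules.
- The section 7.5 statement "Subjects will be followed for adverse events only" might suggest that a non-study transplant removes subjects from both endpoints. Such a transplant is allowed only after visit 21, which is Day 365 after the first transplant. Only a re-transplanted subject can lose final-transplant data this way.
- Graft failure might be equated with non-response. The endpoint is HbA1c plus hypoglycemia, and a subject back on insulin could meet it; section 1.3.1 notes that HbA1c below 7% can coexist with erratic control.
- Nor is every failure lost. Appendix 5 assesses hypoglycemic events monthly, and a recorded severe event makes a subject a non-responder without an HbA1c.

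The setting also limits severity. This is a 10-subject estimation pilot, and its one numerical criterion is on the primary endpoint, which already counts most missing results as failures.

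**Conclusion.** The point holds in a limited form, as something that should be fixed. Section 10.2.2 does not carry the primary endpoint's failure rule over to the secondary responder rates; on its natural reading it lets subjects without a value leave the denominator, at odds with section 10.1. The bias is likely upward. If 5 of 10 respond, the reported rate would be 56% to 83% instead of 50% when one to four failures are dropped; with none dropped there is no difference. These counts are illustrations. The direction rests on missing values belonging mainly to non-responders, which is plausible but not certain.

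Separately, the schedules conflict on HbA1c one year after the last transplant. This reaches only the final-transplant endpoint, and only re-transplanted subjects who stop study treatment. Appendix 5 also contradicts itself on when reduced follow-up ends.

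**What to change.** In section 10.2.2, state that all treated subjects stay in the denominator of both responder endpoints and of the per-center favorable-outcome rate. Count death, withdrawal, loss to follow-up, a non-study transplant before the assessment, or any other missing HbA1c as non-response, in line with the primary endpoint. Where an HbA1c and an event record exist, use them; graft failure alone is not non-response. The planned sensitivity analysis can then show how far this rule drives the result.

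Reconcile Appendix 5 with section 7.5 and Appendix 3 so that HbA1c one year after the last transplant is collected for the final-transplant endpoint, including from subjects on reduced follow-up. Reconcile the two end-of-follow-up statements in Appendix 5.

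The cost is protocol and SAP wording plus one HbA1c sample for a few subjects. Appendix 5 already schedules central-laboratory alloantibody samples every three months, but the one-year quality-of-life contact may be by mail, so timing needs aligning. Reported rates may be slightly lower, and a subject who responded but missed the HbA1c would count as a non-responder.
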